5.5.4 Selection and Timing of Dose for Each Subject

Subjects should take study medication as outlined in Section 5.5.1.

If a subject should forget to administer the injection of study medication on their regularly scheduled dosing date, they should take the forgotten injection as soon as they remember the dose was missed up to the day of their next scheduled dose. The subject should not administer two doses on the same day.

In the event the incorrect dose is taken or a dose is missed, the subject should be instructed to contact the site to determine how to proceed with dosing. The subject must record all dosing information on the Subject Diary/Dosing Log.

Doses not administered (e.g., not taken before next dose is scheduled), should be recorded as not taken in the source. The extra dose should be returned to the study site full. The subject should resume their regular dosing schedule based on the first dosing date at Baseline.

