5.5.6 Treatment Compliance

The Investigator or his/her designated representatives will dispense study drug only for use by subjects enrolled in the study. The study drug must not be used for reasons other than that described in the protocol.

The subject or their qualified designee will administer all doses of study drug. Appropriate site staff will supervise the subject's administration of the study drug at required in-office study visits to ensure proper injection technique. In order to document compliance with the treatment regimen, the subject will be given a subject diary/dosing log (ePRO device) to record all injection dates and times. Compliance information will be documented on the appropriate eCRF. Subjects will be counseled on missed doses of medication. If the subject does not bring the subject diary/dosing log to the site visit and does not return used and unused vials, IP boxes and sharp containers (when applicable), the site should question the subject and obtain as much information as possible as to the dosing of the study drug.

The information should be documented on the source documents as per "best recollection" and when possible, re-verified when the subject diary/dosing log (ePRO device) is returned before completing on the applicable eCRF page.

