- Determine if a subject missed work (based on Q2) in order to analyze the proportion of subjects who missed work:
 - Create a binary (YES or NO) "missed work" variable.
 - A subject will be considered as yes to missed work if Q2 is greater than 0.
 - If Q2 = missing, then MISSED WORK = missing.
 - \circ If Q2 > 0, then MISSED WORK = YES
 - \circ If Q2 = 0, then MISSED WORK = NO
 - Therefore, the proportion of subjects who missed work will be counted based on the number of subjects with MISSED WORK = YES.

Partial Study Dates: If the day and/or month are missing, the following conventions will be used to impute the missing visit (or assessment) dates other than the dosing dates:

- 01 for missing start day,
- End of month for missing end day,

- January 1st will be used for a missing start month,
- December 31st for missing end month.

In case of partially missing AE start and stop dates, the dates will be imputed by comparing to first dose date of study medication so that the corresponding AEs will be made treatment-emergent whenever possible.

In case of missing or partially missing study drug dosing dates, the dates will not be imputed. Subjects will be considered as not receiving dose on that date.

[figure not shown]
Rounding

Rounding will be performed only for presentation of results. No rounding will be performed before or during analyses/calculations. The ROUND function of SAS will be used to round results for presentation.

The mean and median will be rounded for presentation to one decimal more than the data were entered into the database. For example, mean systolic blood pressure will be presented to one decimal place (125.2 mmHg) when it is recorded to integer level in the database (110 mmHg). The standard deviation will be rounded to two decimal places more than the data were entered into the database (e.g., 25.31 mmHg for systolic blood pressure). The minimum and maximum values will be presented as entered into the database.

Probabilities will be rounded to three decimal places before assignment of statistical significance and will be presented in rounded format. Probabilities that round to zero or are reported by SAS as zero will be presented as '< 0.001.'

Percentages will be rounded for presentation to one decimal place; e.g., the proportion 0.1244 will be reported in percent as 12.4%.

Score Definitions

1. Mayo Score and Component Scores

 Table 2.
 Definition of Mayo Score and Component Scores

Term	Definition

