11.2 Analysis of Adverse Events

Treatment-emergent AEs are defined as events with an onset date after the first dose of the study medication (i.e., on/after Rx Day 1) and with an onset date no more than 70 days after the last dose of the study medication. For subjects who roll over into the extension Study M10-870, the window ends prior to first dose date in Study M10-870 (but not more

than 70 days after the last non-missing injection date in Study M11-290). AEs with missing or unknown severity will be categorized as severe. AEs with missing or unknown relationship to study drug will be categorized as 'Reasonable Possibility' of being related to study drug. AEs that are reported more than 70 days after last dose of study drug will be excluded from the treatment-emergent AE summaries; however, they will be included in a separate AE data listing.

Separate Adverse Event Overview tables of number and percentage of subjects in the safety population with treatment-emergent AEs and events per 100 patient-years of induction-exposure and maintenance-exposure (as defined in Section 9.1) will be provided for events during induction period and events during maintenance period (prior to rerandomization due to disease flare if applicable), respectively. AEs that occur after the first dose of study drug in the maintenance period should not be considered treatment-emergent in the induction period, even if they occurred within 70 days of the last dose of study drug in the induction period.

The Adverse Event Overview tables for treatment-emergent AEs in maintenance period (prior to re-randomization due to disease flare if applicable) will also be provided for the RR population. Additionally, an Adverse Event Overview table of events after rerandomization due to first disease flare per 100 PYs of ADA exposure after first disease flare (as defined in Section 9.1) will be provided for the RR population by treatment groups with vs. without re-induction dose (as defined in Section 5.1).

Additionally, an Adverse Event Overview table of adalimumab-treatment-emergent events (i.e., during any ADA exposure throughout the study) per 100 patient-years of overall ADA exposure (as defined in Section 9.1) for patients in the safety population will be provided.

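### SAP 6.0 counts a dose with an incomplete date as not given, which lowers compliance and, if it is the last dose, can shorten exposure and the 70-day adverse-event window by 7 to 14 days

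*SAP*

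**What the plan says.** SAP 6.0, under partial study dates, sets the rule for dosing dates that are missing or incomplete: "the dates will not be imputed. Subjects will be considered as not receiving dose on that date". The sentence just before it treats adverse-event dates differently; partial ones are imputed "so that the corresponding AEs will be made treatment-emergent whenever possible".

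Three later definitions depend on which doses count:

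- **Exposure** (SAP 9.1) is last dose date minus first dose date plus at most 14 days, cut at the first dose of the next period or of the extension study.
- **Compliance** (SAP 9.0) is injections received over injections planned.
- **Treatment-emergent events** (SAP 11.2) are those "with an onset date no more than 70 days after the last dose of the study medication". For children entering the extension study, the window stops before the first dose there, and no later "than 70 days after the last non-missing injection date in Study M11-290".

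The protocol keeps untaken doses distinct. Under 5.5.4, a dose not administered "should be recorded as not taken in the source". Under 5.5.6, if the log and vials do not come back, "the site should question the subject and obtain as much information as possible as to the dosing of the study drug", and the answer is documented from recollection.

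**The concern.** The rule merges two states that the protocol separates: a dose known not to have been taken, and a dose reported as taken whose date is incomplete. A dose reconstructed from recollection is the kind most likely to carry a partial date, and the SAP then removes it.

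At stake are descriptive safety quantities. If the removed dose is the last one, the follow-up window for treatment-emergent events ends too soon and events after the shortened cut-off are left out of the summary tables. Exposure can also be too short, and compliance is too low wherever the removed dose was in fact given. No later SAP text corrects the rule.

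**Working it through.** The documents give no figure that depends on this rule, so there is nothing to reproduce. The check applies the SAP definitions to the planned schedule.

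**Inputs**

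- Nominal day of Week w is 7w + 1 (SAP 6.0 window table: Week 8 is Day 57, Week 52 is Day 365).
- Dosing occasions: Weeks 0, 1, 2, 4 and 6 (5 in induction) and weekly from Week 8 to Week 51 (44 in maintenance), from Protocol Appendix G.
- Week 6 is given at home (Protocol Appendix L). Of the 44 maintenance doses, 6 fall on visits (Weeks 8, 12, 18, 26, 34, 42), so 44 − 6 = 38 are given at home.
- Week 8 non-responders are discontinued (Protocol 5.1), so Week 6 is their last dose.
- Assumed: doses on nominal days, and compliance counted per dosing occasion.

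**Formulas**

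- Exposure = last day − first day + 14, cut where SAP 9.1 says.
- Window end = last day + 70, or the day before the first extension dose if earlier.

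**Results**

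| Case | Exposure in the period | Window ends |
|---|---|---|
| Week 8 non-responder, Week 6 undated | 43 − 1 + 14 = 56 → 29 − 1 + 14 = 42 days | Day 113 → Day 99 |
| Responder entering maintenance, Week 6 undated | induction 56 → 42 days | no change, later doses follow |
| Completer, no rollover, Week 51 undated | 358 − 57 + 14 = 315 → 351 − 57 + 14 = 308 days | Day 428 → Day 421 |
| Completer rolling over on Day 365, Week 51 undated | 365 − 57 = 308 → 308 days | Day 364 → Day 364 |
| Same, Weeks 50 and 51 undated | 308 → 344 − 57 + 14 = 301 days | Day 364 → Day 364 |
| Completer, no rollover, Week 30 undated | 315 → 315 days | Day 428 → Day 428 |

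Compliance for one undated dose that was given, at any position in the period: 4/5 = 80.0% in induction, 43/44 = 97.7% in maintenance.

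**Direction for rates.** With a fixed event count, cutting 56 days to 42 raises a rate per 100 patient-years by 56/42 = 1.33. Events lost from the shortened window pull the other way. The net direction is not fixed.

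**Who could be affected.** At the planning response rate of 75%, non-responders number about 0.25 × 93 ≈ 23. This is the size of the group whose last dose is the Week 6 home dose, not an estimate of how many lack a date.

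**The case against.** The strongest reply is that undated last doses should be rare.

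- Protocol 5.4.1 tells sites to try every means of finding the last-dose date after early discontinuation and to enter it on the eCRF.
- The dosing log is electronic. Protocol 10.3 has entries stored at once and uploaded to a central server, so entries already uploaded survive a device that is never returned.
- Dosing records are checked at each visit (Protocol 5.3.1.1).

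All of this stands and lowers the likely frequency. It does not repair the rule. The SAP does not say that the eCRF date feeds the window or exposure, and if a site recovers only a month, SAP 6.0 discards the dose.

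Other replies also stand in part:

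- Events beyond 70 days remain in a separate listing (SAP 11.2).
- Compliance is descriptive, and SAP 9.0 does not name the source of its numerator.
- The contrast with the adverse-event rule is one of spirit. That rule compares with the first dose date, so it settles the start of the window rather than its end.
- The phrase about extension-study children names the last non-missing injection date only for them. For others the text says simply the last dose.

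The sentence might also be read narrowly, as saying only that no dose is placed on that particular day. When the date is missing there is no particular day, so this reading leaves open whether the dose counts.

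**Conclusion.** The concern holds in a limited form. As written, the rule can drop a dose that was given. Any such dose lowers compliance, if the numerator uses these records. One undated last dose moves the last-dose date back by 7 days in weekly maintenance, or by 14 days at Week 6. The window closes early only for children who do not start the extension study within the 70 days.

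Two stronger readings are tempting and not supported:

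- A reader might infer that every undated dose shortens exposure and the window. A mid-course dose changes neither.
- A reader might also suppose that all home doses after the Week 42 visit are undated. The last dose then moves back 358 − 295 = 63 days, maintenance exposure falls from 315 to 252 days (−20%), and compliance to 35/44. That needs nine consecutive doses given but undated, no recoverable last-dose date and no rollover. Nothing in the documents suggests this is typical, or that the affected children are doing worse than others.

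Because the number of undated doses is not stated, the study-level effect is unknown and may be small. No efficacy endpoint is involved.

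**What to change.** Replace the dosing-date sentences in SAP 6.0 with a rule along these lines:

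1. Count as received every dose with a record that it was given.
2. If its date is incomplete, assign the scheduled dosing day, bounded by the adjacent recorded dose and visit dates and by any known month.
3. For the end of the treatment-emergent window, use the last-dose date on the eCRF (Protocol 5.4.1); failing that, use the latest date consistent with the record.
4. Doses recorded as not taken, and doses with no record of administration, stay not received. Without this limit, exposure and compliance could be overstated.
5. Flag imputed dates and report how many doses and children they concern.

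The cost is a few sentences, a small derivation step and a few imputed dates in the exposure data. The reported count would also show whether the issue mattered.

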4. WPAI

The WPAI was developed to measure the effect of disease on productivity at work and its impact on daily activities. The questions ask about the impact of disease to the patient's caregiver within the past 7 days. Six questions asked on this questionnaire can be described briefly as follows:

Questions:

- Q1. Currently employed (working for pay)? (Yes/No)
- Q2. Hours missed from work due to PROBLEM.
- Q3. Hours missed due to other reasons.
- Q4. Hours actually worked.
- Q5. Degree PROBLEM affected productivity while working.

Q6. Degree PROBLEM affected regular activities other than job.

WPAI scores are expressed as percent impairment based on the above questions. The four main impairment measures or scores are derived as follows:

Scores:

S1. Absenteeism: Percent work time missed due to PROBLEM:

$$100 \times \left[\frac{Q2}{Q2 + Q4} \right]$$

S2. *Presenteeism*: Percent impairment while working due to PROBLEM:

$$100 \times \left\lceil \frac{Q5}{10} \right\rceil$$

S3. Percent *overall work impairment* due to PROBLEM:

$$100 \times \left[\frac{Q2}{Q2 + Q4} + \left\{ 1 - \frac{Q2}{Q2 + Q4} \right\} \times \frac{Q5}{10} \right]$$

S4. Percent *activity impairment* due to PROBLEM: $100 \times \left\lceil \frac{Q6}{10} \right\rceil$

5. Other

[figure not shown]
Body Mass Index (BMI, in kg/m^2) will be obtained as: BMI = weight (kg)/(height [m] × height [m])

"z" score for height velocity will be obtained as: (Observed height velocity [cm/yr] – mean height velocity for age and sex [cm/yr]/[SD of the mean]). NOTE: The mean and Standard Deviation (SD) will come from published table values:

The CDC Growth Charts webpage of the Center for Disease Control and Prevention with derivation details on the "z" score:

http://www.cdc.gov/growthcharts/percentile_data_files.htm, STATAGE.xls ('stature-for-age-chart', for height) to be used.

Inappropriate Tanner stage will be defined depending on age and sex as follows: girls ≥ 14 years/boys ≥ 15 of age with a Tanner stage of 1; girls ≥ 16 years/boys ≥ 18 of age with a Tanner stage < 4; girls ≥ 19 years/boys ≥ 19 of age with a Tanner stage of < 5.

7.0 Demographics, Baseline Characteristics, Medical History, and Previous/Concomitant Medications

All demographic and Baseline summaries, medical history, and prior/concomitant medications will be provided for the ITT, ITT-E, mITT, mITT-E, RR and safety population by treatment groups defined in Section 5.1, unless otherwise specified.

[figure not shown]

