An x-ray of the wrist for the assessment of bone age will be obtained at Screening and at Week 52/Premature Discontinuation visit to determine changes in bone maturation. Sites should use the Greulich and Pyle method for reading the x-ray.²⁰ The x-ray report requires the signature of the radiologist who read the films or of the investigator. The bone age that is determined by the x-ray should be recorded on the eCRF. Assessment of bone age will not be required for subjects with the Premature Discontinuation visit at or before Week 26. An x-ray of the wrist for the assessment of bone age at Screening will

not be required if the subject had an x-ray within 90 days of Screening, provided all protocol required documentation is available at the site.

Anthropometric Evaluations

Height and weight obtained at Baseline, Week 26 and Week 52/Premature Discontinuation will be used by AbbVie Data Management and Statistical groups for determination of BMI and "z" score (observed height velocity [cm/yr] – mean height velocity for age and sex [cm/yr]/SD of the mean) for height.

At Baseline, height from 6 months prior to Screening and maximal weight attained within preceding 6 months will be recorded.

Tanner Stage

Tanner Stage will be assessed at Screening (or at Baseline as appropriate), Week 26 and Week 52/Premature Discontinuation Visit if premature discontinuation occurs after Week 26. Tanner Staging should be captured on the appropriate eCRF page.

Pediatric Ulcerative Colitis Activity Index (PUCAI)

A PUCAI score will also be calculated at all study visits beginning at Baseline.

An example of the PUCAI is located in [Appendix C](#).

The PUCAI score will be assessed using subject-reported symptoms and activity level. The answers should reflect symptoms and activity level during the previous 24 hours. The PUCAI scores of the last 2 days prior to each study visit will be averaged and used for the PUCAI scores for each study visit. The total PUCAI score will be rounded up to the next 5-point interval as applicable. In order to account for unavailable or excluded diary entries as per the provisions given below diary entries for the PUCAI score of the most recent 2 days within 10 days prior to each study visit will be used.

Diary entries of the following days should not be included in the 2 days prior to the visit that are evaluated for the PUCAI score: (1) the day the subject received medication for

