5.3.3.2 Secondary Variables

Ranked secondary efficacy variables are:

1. Proportion of subjects in Mayo clinical response at Week 52 in Week 8 responders per PMS;
2. Proportion of subjects who achieve mucosal healing at Week 52 as measured by Mayo endoscopy subscore (defined as ≤ 1) in Week 8 responders per PMS;
3. Proportion of subjects who achieve Mayo clinical remission at Week 52 in Week 8 remitters per PMS;
4. Proportion of subjects receiving corticosteroid at Baseline who have discontinued corticosteroid prior to Week 52 and are in Mayo clinical remission at Week 52 in Week 8 responders per PMS.

Additional exploratory secondary analyses will be performed for:

- Proportion of subjects in PMS clinical remission at Week 52 in Week 8 responders per PMS;
- Proportion of subjects in PUCAI remission (defined as < 10) at Week 8;
- Proportion of subjects in PUCAI response (defined as a decrease in PUCAI ≥ 20 points from Baseline) at Week 8;

- Proportion of subjects in PUCAI remission (defined as < 10) at Week 52 in Week 8 responders per PMS;
- Proportion of subjects in PUCAI response (defined as a decrease in PUCAI ≥ 20 points from Baseline) at Week 52 in Week 8 responders per PMS;
- Proportion of subjects receiving corticosteroid at Baseline who discontinue corticosteroid prior to Week 52 and are in PUCAI remission at Week 52 in Week 8 responders per PMS;
- Change from Baseline in total IMPACT III Quality of Life scores over time for subjects at least 9 years old at Baseline;
- Change from Baseline in WPAI scores over time;
- Change from Baseline in "z" scores for height (observed height velocity [cm/yr] – mean height velocity for age and sex [cm/yr]/SD of the mean) at Week 26 and Week 52;
- Change from Baseline in BMI at Week 26 and Week 52;
- Change from Baseline in "z" scores for weight-for-age at Week 26 and Week 52;
- Proportion of subjects at appropriate Tanner stage at Week 26 and Week 52 compared to Baseline;
- Proportion of subjects in PMS response over time;
- Proportion of subjects in PMS remission over time;
- Proportion of subjects in PUCAI response over time;
- Proportion of subjects in PUCAI remission over time;
- Change from Baseline in number of daily stool over time;
- Change from Baseline in albumin and total protein at different time points;
- Change from Baseline in hemoglobin, hematocrit, red blood cell count at different time points;
- Change from Baseline in hs-CRP levels at different time points;

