10.4 Secondary Efficacy Analyses

[figure not shown]
The secondary efficacy endpoints are divided into two groups. The first group consists of ranked secondary efficacy endpoints. The second group includes all other secondary efficacy endpoints and special assessments.

The ranked secondary efficacy endpoints in hierarchical order are:

[figure not shown]
- Proportion of subjects in Mayo clinical response at Week 52 in Week 8 responders per PMS;
- Proportion of subjects who achieve mucosal healing at Week 52 as measured by Mayo endoscopy subscore (defined as ≤ 1) in Week 8 responders per PMS;
- Proportion of subjects who achieve Mayo clinical remission at Week 52 in Week 8 remitters per PMS;
- Proportion of subjects receiving systemic corticosteroids (UC related or non-UC related) at Baseline who have discontinued systemic corticosteroids prior to Week 52* and are in Mayo clinical remission at Week 52 in Week 8 responders per PMS.

Additional exploratory secondary analyses will be performed for:

[figure not shown]
- Proportion of subjects in PMS clinical remission at Week 52 in Week 8 responders per PMS;
- Proportion of subjects in PUCAI remission (defined as < 10) at Week 8;
- Proportion of subjects in PUCAI response (defined as a decrease in PUCAI
 ≥ 20 points from Baseline) at Week 8;

- Proportion of subjects in PUCAI remission (defined as < 10) at Week 52 in Week 8 responders per PMS;
- Proportion of subjects in PUCAI response (defined as a decrease in PUCAI
 ≥ 20 points from Baseline) at Week 52 in Week 8 responders per PMS;
- Proportion of subjects receiving systemic corticosteroids at Baseline who discontinue systemic corticosteroids prior to Week 52* and are in PUCAI remission at Week 52 in Week 8 responders per PMS;
- Change from Baseline in total IMPACT III Quality of Life score and subscores over time for subjects at least 9 years old at Baseline;
- Change from Baseline in WPAI scores over time;
- Change from Baseline in "z" scores for height at Week 26 and Week 52;
- Change from Baseline in BMI at Week 26 and Week 52;
- Change from Baseline in "z" scores for weight-for-age at Week 26 and Week 52;
- Proportion of subjects at appropriate Tanner stage (see Section 6.0) at Baseline, Week 26 and Week 52 (OC analysis);
- Proportion of subjects in PMS response over time;
- Proportion of subjects in PMS remission over time;
- Proportion of subjects in PUCAI response over time;
- Proportion of subjects in PUCAI remission over time;

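### The SAP standardises height velocity (cm/yr) but takes the mean and SD from a stature-for-age table, and divides only the mean by the SD, so the exploratory height endpoint is not a z-score as written

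*SAP*

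**What the plan says.** SAP 6.0, Score Definitions, item 5 (Other), introduces a z-score for height velocity and gives the expression "Observed height velocity [cm/yr] – mean height velocity for age and sex [cm/yr]/[SD of the mean", with the round bracket closing only after the SD. The next sentence adds that "The mean and Standard Deviation (SD) will come from published table values". The source is then given as a CDC growth-chart page, with the instruction "STATAGE.xls ('stature-for-age-chart', for height) to be used".

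The protocol defines the endpoint on velocity as well. Section 5.3.3.2 has "observed height velocity [cm/yr] – mean height velocity for age and sex [cm/yr]/SD of the mean) at Week 26 and Week 52", placed in brackets after the label of z-scores for height. The same expression appears in the Synopsis (1.2) and under Anthropometric Evaluations in 5.3.1.1. That last section also has sites record, at Baseline, a height from six months before Screening.

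SAP 10.4 lists the endpoint among the additional exploratory secondary analyses as change from Baseline in z "scores for height at Week 26 and Week 52". Velocity is not mentioned there.

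**The concern.** A z-score needs one quantity, a reference mean and SD for that same quantity, and the SD dividing the whole difference. The SAP text fails on two counts. The quantity is a rate in cm/yr while the named table is for attained height, and the SD divides the mean alone. The labels do not settle which quantity is meant: the SAP definition and the protocol formula say velocity, whereas the named table and the SAP 10.4 label say height.

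Growth matters in this population. Protocol 3.2 says that therapy of paediatric UC should have no adverse effect on linear growth, and this is the only height-growth z-score listed. With the present text, two programmers could reach incompatible results, each able to point to some part of the plan.

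**Working it through.** The plan states no figure for this endpoint, so there is nothing to reproduce. The documents also give no reference means or SDs. All numerical inputs below are therefore assumed, and serve only to show scale. That the stature table is in cm is inferred from its label.

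**Notation.** v = observed velocity; m, s = reference mean and SD.
- As typed: v - m/s
- Bracket corrected: (v - m)/s

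**1. Velocity formula with a stature reference.** Assume v = 5 cm/yr.

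| m (cm) | s (cm) | As typed | Bracket corrected |
|---|---|---|---|
| 105 | 5 | 5 - 105/5 = -16.0 | (5 - 105)/5 = -20.0 |
| 140 | 7 | 5 - 140/7 = -15.0 | (5 - 140)/7 = -19.3 |
| 170 | 8 | 5 - 170/8 = -16.3 | (5 - 170)/8 = -20.6 |

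Varying v over 2 to 8 cm/yr, with references 105/4.5, 135/6 and 165/7 cm, gives -14.5 to -21.6 as typed and -21.2 to -23.3 with the bracket corrected. No combination can be read as a z-score.

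**2. Bracket alone, with a matched velocity reference.** Assume v = 5, m = 6, s = 1.5 cm/yr.
- As typed: 5 - 6/1.5 = +1.00
- Bracket corrected: (5 - 6)/1.5 = -0.67

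A child growing more slowly than the reference mean is scored above it.

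**3. Change from Baseline.** Assume the stature reference moves from 135/6 to 138/6.2.
- Velocity rising from 3 to 6, as typed: (6 - 138/6.2) - (3 - 135/6) = +3.24
- Same, bracket corrected: (6 - 138)/6.2 - (3 - 135)/6 = +0.71
- Velocity constant at 5, as typed: (5 - 138/6.2) - (5 - 135/6) = +0.24
- Same, bracket corrected: (5 - 138)/6.2 - (5 - 135)/6 = +0.22

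If instead the reference mean moves from 135 to 141 with SD fixed at 6, at constant velocity 5, the score shifts by -6/6 = -1.0 in either form. If the SD rises to 6.3 as well, the shift is about +0.1. Differencing does not restore a z-score scale, and the sign of the drift depends on the assumed SDs.

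**4. Consistent versions, for comparison.**
- Height against stature (135/6 cm): heights of 130, 135 and 141 cm give -0.83, 0.00 and +1.00.
- Velocity against velocity (6/1.5 cm/yr): velocities of 2, 5 and 8 give -2.67, -0.67 and +1.33.

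**The case against.** The best defence is that the plan is ambiguous rather than unusable. The SAP 10.4 label, the named table and the pointer to a page with z-score derivation details all fit an ordinary height-for-age z-score; on that view the velocity line was carried over from the protocol. The bracket looks like a slip that a programmer would correct unprompted, and a group mean near -20 would be noticed at once. The endpoint is one of a long exploratory list, is not among the high-versus-standard comparisons, and sits beside BMI, weight-for-age z and Tanner stage.

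Most of this stands as a limit on importance. It does not remove the conflict: the SAP's only explicit definition is on velocity, the protocol agrees with it, and the extra pre-Screening height makes velocity a plausible intention. Nothing elsewhere in either document says which governs.

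Three stronger readings are not supported:
- A reader might infer that the change from Baseline would falsely suggest growth failure because the reference mean rises with age. In the illustration m/s is nearly constant (20 to 21.25), and at constant velocity the change ranges from -1.0 to about +0.2 according to the SDs assumed. No direction can be claimed.
- A reader might take the SD wording in the formula as a standard error. The SAP's next sentence says that the SD comes from published tables, which answers this.
- A reader might conclude that height-for-age must be the endpoint. The protocol defines velocity, so that choice belongs to the sponsor.

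**Conclusion.** The point holds as a specification error in an exploratory endpoint. The SAP pairs a velocity formula with a table it labels as stature, and the bracket is wrong in both documents. Taken literally, the result lies some 15 to 21 units below zero on the assumed inputs (velocity 5 cm/yr; stature 105 to 170 cm; SD 5 to 8 cm). With a matched reference, the bracket alone can reverse the sign. Change from Baseline would not be interpretable on a z-score scale, in either direction. The table mismatch is the substantive fault; the bracket is probably typographical. The mismatch rests on the SAP's own label for the file, since the documents do not show its columns or units. The co-primary and ranked secondary tests are unaffected, so this should be corrected but does not threaten the trial's main conclusions.

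**What to change.** The sponsor should state which quantity is intended, then make formula, reference table and label agree in SAP 6.0 and 10.4 and in protocol 1.2, 5.3.1.1 and 5.3.3.2. There are two acceptable routes:

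- **(a) Height-for-age z-score.** Compare measured height with the age- and sex-specific stature-for-age reference at Baseline, Week 26 and Week 52, then take change from Baseline. This needs wording only: the heights are already scheduled (protocol 5.3.1.1), and age and sex are recorded (SAP 7.1).
- **(b) Height-velocity z-score.** Use (observed velocity - reference mean velocity)/reference SD. Name a velocity reference table, state the interval over which velocity is annualised at each time point, and use the height from six months before Screening for the Baseline value. Beyond wording, this needs a velocity reference, which neither document names at present.

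Under either route, close the bracket before the division and describe the divisor as the SD of the reference population.
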